6.4.3. Secondary/other/exploratory analysis

All secondary efficacy endpoints will be summarized by descriptive statistics for each treatment group, for each time point, including summaries of change from baseline when applicable.

Values for all endpoints that are collected daily using the eDiary (from Section 6.4.3.1 to Section 6.4.3.24) will be based on the 28 calendar days immediately prior to and including the day of the corresponding visit or prior to and including the last treatment administration date for Month 12, or the 28 calendar days immediately prior to and including the last dose date for subjects who discontinue treatment prior to the visit in question (or fewer if treatment is stopped less than 4 weeks after first dose date), in order to estimate the treatment effect while under treatment. The last 28 days on treatment will be used at all subsequent scheduled visits for those discontinued subjects. Descriptive summaries for each 28-day period will be performed in two ways however:

- Once including only values of 28 days prior to Month X, i.e. using the last 28 days prior to Month X eCRF visit date for subjects who have not discontinued up to that month. If subjects discontinued prior to Month X the corresponding value will be missing from the summary at Month X;
- Once applying the while on treatment strategy, i.e. using the last 28 days prior to Month X eCRF visit date for subjects who have not discontinued up to that month, and for subjects who discontinued prior to Month X, the last 28 days prior to treatment discontinuation will be used. For all subsequent timepoints (Month X+1, etc.) the same last 28 days prior to treatment discontinuation will be used.

Corresponding baseline values will be calculated based on the two baseline menstrual cycles, which may not be exactly 28 days each.

The values for other endpoints (monthly and 3-monthly questionnaires from Section 6.4.3.25 to Section 6.4.3.32) are defined as the value at the corresponding visit or value falling into the corresponding visit window as described in section 5.5. For these other endpoints, descriptive summaries by visit will be performed in two ways, once including values at the corresponding visit or value falling into the corresponding visit window as described in section 5.5, and once applying the while on treatment strategy, i.e., including values from the discontinued visits at each next scheduled visit.

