For endpoints based on daily ediary data, analyses will use observed data only in such cases, provided that a minimum number of 43% (at least 12 days of each 28-day period) completed daily eDiary entries are available. Subjects who have less than the minimum number of days available will be excluded from the analysis. This is valid under the assumption that such data is MAR, conditional on the baseline value.

6.4.3.1. Change from baseline to Month 12 in DYS (VRS) and in NMPP (VRS)

Mean pelvic pain scores for DYS and for NMPP for each subject will be calculated in the same way as for the primary endpoints. The change from baseline to Month 12 (the last 28 days of randomized treatment up to the Month 12 visit, will be defined as the last 28 days prior to and including the last treatment administration date as defined in Section 5.2.1, or the 28 calendar days immediately prior to and including the last dose date for subjects who discontinue treatment prior to Month 12) in DYS using the VRS, and the change from baseline to Month 12 (the last 28

days of randomized treatment up to the Month 12 visit, will be defined as the last 28 days prior to and including last treatment administration date as defined in Section 5.2.1 or the 28 calendar days immediately prior to and including the last dose date for subjects who discontinue treatment prior to Month 12) in NMPP using the VRS.The mean pelvic pain scores for DYS and NMPP and change from baseline will be descriptively summarized. Summary will be repeated on the Per Protocol Extension Analysis Set.

Cumulative distribution functions (CDF) for change from baseline at Month 12 for DYS and NMPP will be provided, with separate lines for each treatment group. The x-axis will present the different values for the DYS or NMPP change from baseline, and the y-axis will present the proportion of subjects reaching each value of change. Vertical lines of the relevant responder thresholds will be displayed on the plots.

6.4.3.2. Change from baseline to Month 12 in dyschezia (Numeric Rating Scale - NRS)

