A03EA	Antispasmodics, psycholeptics and analgesics in combination
С0ЗАН	Thiazides, combinations with psycholeptics and/or analgesics
M01	Anti-inflammatory and anti-rheumatic products
M02	Topical products for joint and muscular pain
M03	Muscle relaxants
N02	Analgesics
N07BC	Drugs used in opioid dependence
S02DA	Analgesics and anesthetics

Among those analgesic medications, all medications with Pharmacological Subgroup (3rd level of the ATC classification) equal to 'OPIOIDS' (ATC code = N02A) will be considered as opiate medications. Other analgesic medications will be considered as non-opiate medications.

In addition to analyzing the absence of analgesic use for EAP, the amount of analgesics used for each 4-week period up to Month 12 will be summarized as a continuous variable, including the change from baseline. This analysis will be based on e-diary data only, as subjects did not record analgesic intake in the concomitant medication page on a tablet-by-tablet basis.

Due to a low number of subjects using any opioids, opioids use will not be analyzed as a continuous variable, only a listing with by subject opioid use mean daily pill count will be provided.

The baseline amount of analgesic used will be computed by averaging the amount used during the two baseline menstrual cycles.

Summary will be repeated on the Per Protocol Extension Analysis Set.

6.4.3.7. Responder rate at scheduled visit other than Month 12 visit, for DYS and NMPP (VRS)

The responder rate at each scheduled visits other than Month 12 visit, for DYS and NMPP will be analyzed the same way as described for the primary analysis endpoint in Section 6.4.2.

6.4.3.8. Change from baseline to each scheduled assessment in mean pelvic pain scores for DYS, NMPP and overall pelvic pain, during the previous 4-week period assessed on the NRS and VRS

The change from baseline to each scheduled assessment in mean pelvic pain scores for DYS, NMPP and overall pelvic pain will be descriptively summarized.

6.4.3.9. Change from baseline to each scheduled assessment in the number of days with moderate to severe pelvic pain during the previous 4-week period assessed on the VRS

The actual value and change from baseline of number of days with moderate or severe pelvic pain collected in the e-diary on the VRS will be summarized for each 28-day period. The baseline value will be computed by averaging the number of days with moderate or severe pelvic pain of the two baseline menstrual cycles.

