6.4.3.16. Change from baseline to each scheduled assessment in the number of days of opioid analgesic use for EAP during the previous 4-week period as assessed in the eDiary

The actual value and change from baseline in the number of days with opioid analgesic use for EAP collected in the e-diary will be calculated for each 28-day period. The baseline value will be computed by averaging the number of days with opioid analgesic use of the two baseline menstrual cycles.

Due to a low number of subjects using any opioids, number of days with opioid analgesic use will not be analyzed, only a by subject listing will be provided.

6.4.3.17. Change from baseline to each scheduled assessment in the number of pelvic pain-free days (assessed on the VRS) during the previous 4-week period

The actual value and change from baseline of number of pelvic pain-free days collected in the ediary will be summarized for each 28-day period. The baseline value will be computed by averaging the number of pelvic pain-free days of the two baseline menstrual cycles.

6.4.3.18. Change from baseline to each scheduled assessment in ability to perform daily activities during the previous 4-week period, as assessed in the eDiary (daily function NRS)

Daily activities score for each subject will be calculated by averaging over the corresponding 28 calendar days immediately prior to and including the day each visit (or the 28 calendar days

immediately prior to and including the last dose date for subjects who discontinue treatment prior to Month 12). The baseline mean of daily activities score will be calculated by averaging over the two baseline menstrual cycles. The actual value and change from baseline of daily activities score will be summarized as a continuous variable.

6.4.3.19. Change from baseline to each scheduled assessment in the number of days with no difficulty in doing daily activities due to EAP during the previous 4-week period as assessed in the eDiary (daily function NRS)

The actual value and change from baseline of number of days with no difficulty in doing daily activities due to EAP collected in the e-diary will be summarized for each 28-day period. The baseline value will be computed by averaging the number of days of the two baseline menstrual cycles.

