6.4.3.20. Change from baseline to each scheduled assessment in the number of days when dyspareunia was a problem during the previous 4-week period (including days when sexual intercourse was avoided because of anticipation of pain) as assessed on the dyspareunia VRS

The actual value and change from baseline of number of days with answer to Sexual Intercourse in the last 24H questionnaire is "Intercourse was interrupted due to pain" or "No, I avoided sexual intercourse because of anticipation of pain" collected in the e-diary will be summarized for each 28-day period. The baseline value will be computed by averaging the number of days of the two baseline menstrual cycles.

6.4.3.21. Change from baseline to each scheduled assessment in the number of days when sexual intercourse was avoided because of anticipation of pain during the previous 4-week period as assessed on the dyspareunia VRS

The actual value and change from baseline in the number of days with answer to Sexual Intercourse in the last 24H questionnaire is "No, I avoided sexual intercourse because of anticipation of pain" collected in the e-diary will be summarized for each 28-day period. The baseline value will be computed by averaging the number of days of the two baseline menstrual cycles.

In addition, the proportion of days when sexual intercourse was avoided because of anticipation of pain will be also summarized for actual values and changes from baseline.

The proportion is defined as:

Number of days when sexual intercourse was avoided because of anticipation of pain/ (Number of days in period – Number of days with missing data – Number of days with no sexual intercourse for other reasons)

The number of days in each period will be equal to 28, except at baseline, for which it will be the number of days in each baseline menstrual cycle.

6.4.3.22. Change from baseline to each scheduled assessment in the number of days with uterine bleeding (including spotting) during the previous 4-week period measured by eDiary

The actual value and change from baseline in the number of days with uterine bleeding ("Bleeding", "Spotting", "Heavy Bleeding") collected in the e-diary will be summarized for each 28-day period. The baseline value will be computed by averaging the number of days with uterine bleeding during the two baseline menstrual cycles.

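### Eight of the nine summarized day-count endpoints have no version based on answered days, so change from main baseline can mix symptoms with days observed

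*SAP*

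**What the plan says.** SAP 6.4.3 defines ten diary endpoints as a number of days. Opioid days (6.4.3.16) are not summarized: "number of days with opioid analgesic use will not be analyzed, only a by subject listing will be provided". The other nine are:

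- moderate or severe pain (6.4.3.9)
- any analgesic use (6.4.3.15)
- pain-free days (6.4.3.17)
- no difficulty with activities (6.4.3.19)
- dyspareunia a problem (6.4.3.20)
- intercourse avoided (6.4.3.21)
- uterine bleeding (6.4.3.22)
- school or work missed (6.4.3.23)
- in bed or lying down (6.4.3.24)

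After baseline, each is the number of days in a 28-day period. At baseline each is the plain average of two cycle counts. In 6.4.3.9: "The baseline value will be computed by averaging the number of days with moderate or severe pelvic pain of the two baseline menstrual cycles". In 6.4.3.17: "The baseline value will be computed by averaging the number of pelvic pain-free days of the two baseline menstrual cycles". The opening of 6.4.3 adds: "Corresponding baseline values will be calculated based on the two baseline menstrual cycles, which may not be exactly 28 days each". Diary data are used as observed, "provided that a minimum number of 43% (at least 12 days of each 28-day period) completed daily eDiary entries are available".

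Only 6.4.3.21 also has a proportion. Its denominator is "Number of days in period – Number of days with missing data", less "Number of days with no sexual intercourse for other reasons". The period length is 28 "except at baseline, for which it will be the number of days in each baseline menstrual cycle". The other eight endpoints have nothing comparable. Analgesic pill counts (6.4.3.13) and the co-primary pain scores (6.4.2.1) are already daily means. The repeats at 21 and 10 completed days (6.4.2.1.1) are stated for the primary analysis only.

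SAP 6.4 says that efficacy endpoints are derived as in the main study. That study's SAP is not among the documents.

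**The concern.** For a mean, dropping blank days removes them from the numerator and the denominator. A count has no denominator, so a dropped day lowers it just as an event-free day would. More blanks on treatment than at baseline make bad-day counts look better, and make pain-free and no-difficulty days look worse. More blanks at baseline do the reverse. A baseline cycle longer or shorter than 28 days shifts the change even with complete diaries, although the protocol (7.1.2) frames these endpoints over a 4-week period.

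Unequal completion is foreseeable. SAP 6.2.6.3 sets aside extension diaries that some non-US subjects completed in English because of a device error, and SAP 6.4.2.2 expects incomplete data from Ukraine. Neither says how many subjects are affected.

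The extension has no placebo arm after Month 6 and no hypothesis tests, so these results will be read as within-group change. At stake is whether a change in days reflects symptoms or diary entries.

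**Working it through.** **The plan's own figure.** 12/28 = 42.86%, which rounds to the stated 43%.

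**Count.** Ten endpoints defined, less 6.4.3.16 (listing only), leaves nine. One (6.4.3.21) has a scaled companion, so eight do not.

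**Formula.** Let p be the daily event rate, unchanged from baseline to treatment, and n the days that can contribute. If blanks are unrelated to symptoms, the expected raw count is p x n, and

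false change = p x (n on treatment - n at baseline).

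The documents give no p, completion rate or cycle length. The values below are assumptions, chosen to show a range.

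| n at baseline | n on treatment | p = 0.10 | 0.25 | 0.50 | 0.75 |
|---|---|---|---|---|---|
| 28 | 25 | -0.3 | -0.75 | -1.5 | -2.25 |
| 28 | 21 | -0.7 | -1.75 | -3.5 | -5.25 |
| 28 | 12 (permitted minimum, extreme) | -1.6 | -4 | -8 | -12 |
| 24 | 18 | -0.6 | -1.5 | -3 | -4.5 |
| 21 | 21 | 0 | 0 | 0 | 0 |
| 35 (long cycle, full diary) | 28 | -0.7 | -1.75 | -3.5 | -5.25 |
| 24 (short cycle, full diary) | 28 | +0.4 | +1 | +2 | +3 |

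Example: 0.50 x (21 - 28) = -3.5 days. Under the same assumptions, 28 x (event days / answered days) has an expected change of 0 in every row.

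**Bleeding days cluster**, so a constant rate need not apply. Assume 5 consecutive bleeding days per cycle and a 28-day window equally likely to start anywhere. With 35-day cycles the window holds 5 x 28/35 = 4.0 days on average, a change of -1.0 (range -5 to 0). With 24-day cycles it holds 5 x 28/24 = 5.83, a change of +0.83 (range 0 to +4).

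**Month 6 against Month 12, same subjects.** Both changes subtract the same baseline B:

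(p x n12 - B) - (p x n6 - B) = p x (n12 - n6).

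Baseline cycle length and baseline blanks drop out. Only a difference in on-treatment completion remains.

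**Limits of scaling.** Let a and b be the entry probabilities on event days and other days, with a full 28-day baseline. Raw error = 28p(a - 1). Scaled error = 28[pa/(pa + (1-p)b) - p]. At p = 0.5:

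- a = 0.5, b = 0.8: raw -7.0, scaled -3.2
- a = 0.8, b = 0.5: raw -2.8, scaled +3.2

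In the second case scaling has the larger error, with the opposite sign.

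**Noise.** Sampling entries without replacement, with 14 event days in 28, the scaled count has an SD of (28/12) x sqrt(12 x 0.25 x 16/27) = 3.1 days at 12 entries and 1.6 at 21. With 3 event days the SDs are 1.9 and 1.0.

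**The case against.** The primary objective is maintenance of efficacy in women already treated for 6 months. For that question the baseline part of the problem cancels, as shown. Cycle length also plays no part where Baseline 2 is used, because for diary endpoints it is the last 28 days of main-study treatment (SAP 6.2.2). Both points stand and narrow the concern to change from main baseline and to unequal on-treatment completion.

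The main-study SAP may contain a scaling rule. That also stands: the gap may be only a missing cross-reference.

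The protocol defines these endpoints as numbers of days, so a raw count can be defended, and 4.0 bleeding days rescaled from 5 in a 35-day cycle is not a number any subject experienced. This is a reason to keep the raw count alongside, but it does not remove the mixing of symptoms with days observed.

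Protocol 10.3.1 plans daily alarms and compliance checks, and daily means for pelvic pain (6.4.3.8), function (6.4.3.18) and pills (6.4.3.13) are also reported. These lessen the consequence, although bleeding days and missed-work days have no such companion.

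Two stronger readings are tempting. A reader might infer that the SAP prescribes counting blanks as event-free. It does not. It says so explicitly for drug intake (4.1, 6.3.8.2) but is silent here, and the effect follows only from the arithmetic of a count. A reader might also infer that 6.4.3.20 is defective because it does not say whether days not sexually active for other reasons belong to its base. A raw count has no base, so that question arises only once a denominator is introduced.

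**Conclusion.** The point holds as a cheap improvement. For eight summarized secondary endpoints, change from main baseline mixes symptoms with days observed whenever completion or window length differs. For 6.4.3.21 the existing proportion already addresses this.

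The tabulated sizes show what is possible under constant event rates and blanks unrelated to symptoms. They are not estimates of bias in this trial. A reader might infer that the counts favor linzagolix. The documents do not support that: no completion rates are given, the sign depends on where the blanks fall and on whether the endpoint counts good or bad days, and equal completion over equal windows gives no error.

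No formal test uses these counts, and the co-primary endpoints, built on daily means, are not affected.

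**What to change.** If the main-study SAP already scales these counts, state that rule in SAP 6.4.3. Otherwise:

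- For 6.4.3.9, 6.4.3.15, 6.4.3.17, 6.4.3.19 and 6.4.3.22 to 6.4.3.24, summarize 28 x (event days / days with a non-missing answer), per baseline cycle and then averaged, and per on-treatment period. Keep the 12-day minimum.
- For analgesic days, first fill a missing entry from the next day's answer, as SAP 6.2.6.3 provides.
- Derive main-study visits shown in the same tables the same way, and keep the raw count alongside for consistency with the main study.
- For 6.4.3.20, add a companion proportion with the 6.4.3.21 denominator. Scaling it to 28 days would turn one event in 4 eligible days into 28 x 1/4 = 7 days. For 6.4.3.21 the existing proportion suffices.
- State that scaling assumes blanks are unrelated to symptoms, and that values from few entries are noisier.

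The cost is one rule, one denominator in the derivation of eight endpoints, and re-derivation of the main-study visits. Tables grow: diary endpoints are already summarized two ways, so raw plus scaled makes four. No new data are needed and no subject is lost.

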6.6. Safety Evaluations

Summaries will be performed using the Extension Safety Analysis Set and the Follow-up Extension Safety Analysis Set.

Data from the main study (i.e. before Month 6), the extension study and the Month 6 Extension follow-up will be summarized and listed as relevant

6.6.1. Adverse Events

All AEs recorded during the course of the study will be coded according to the MedDRA dictionary (26.0) and assigned to a system organ class (SOC) and Preferred Term (PT). The NCI-CTCAE (version 4.3) will be used to grade the severity of AEs.

The following definitions will be used for the analysis of adverse events (AEs). All analysis described below will be based on the Treatment Emergent Adverse Events (TEAEs), unless otherwise specified.

	Definition
Treatment emergent adverse event (TEAE)	AEs with a start date on or after the first dose of extension study drug through 30 days after discontinuation of study drug or Month 12 visit date, or any event that was present at Month 6 but worsened in intensity or was subsequently considered drug- related by the investigator through the end of the extension study
Treatment Related TEAE/AEs	LGX-related AEs, defined as having "definite, probable or possible" relationship to study drug ABT-related AEs, defined as having "definite, probable or possible" relationship to add-back therapy
Serious Adverse Events (SAEs)	Any AE with "Serious?" = Yes in the CRF "Adverse event" page.
Adverse Events Leading to Permanent Treatment Discontinuation	Any AE action taken = Drug Withdrawn in the CRF "Adverse event" page.
Adverse Events Leading to Death	Any AE with fatal outcome

Post-Treatment Adverse Events	Adverse events starting more than 30 days
	after end of treatment

TEAEs tables will be presented for the below periods/populations:

- Extension treatment period on Extension Safety Analysis Set
- Extension follow-up period on Follow-up Safety Analysis Set,
- Combined Extension treatment and follow-up period on Follow-up Safety Analysis Set
- Combined Main treatment period and Extension treatment period on Extension Safety Analysis Set:
- Combined Main treatment period and Extension treatment period on Safety Analysis Set
- Day 1 (from main study) to end of Extension follow-up period, or end of Main follow-up period for subjects not entering extension, on Safety Analysis Set

Post-treatment AEs tables will be presented for below periods/populations:

- Combined Extension treatment and follow-up period on Follow-up Safety Analysis Set
- Extension follow-up period on Follow-up Safety Analysis Set
- Day 1 (from main study) to end of Extension follow-up period, or end of Main follow-up period for subjects not entering extension, on Safety Analysis Set

All AEs tables will be presented for the below periods/populations:

- Day 1 (from main study) to end of Extension follow-up period, or end of Main follow-up period for subjects not entering extension, on Safety Analysis Set

Periods are defined in section 5.2

Tables based on Safety Analysis Set will use the following treatment groups, with the note that subjects can have a different time of treatment exposure (up to 6 months for subjects not in extension, up to 12 months for subjects entering extension):

- linzagolix 75 mg / linzagolix 75 mg
- linzagolix 200 mg with ABT / linzagolix 200 mg with ABT
- Placebo / linzagolix 75 mg (subject receiving placebo in main study and treated with linzagolix 75 mg in extension study)
- Placebo / linzagolix 200 mg with ABT (subject receiving placebo in main study and treated with linzagolix 200 mg with ABT in extension study)
- Placebo

If, for a subject not entering the Extension follow-up period, an AE occurs after Month 12-1 or treatment discontinuation, then the AE will be counted in the Extension treatment period.

For all study periods, an overall summary table will be prepared presenting, by treatment group, the number and percentage of subjects with

- any AE,
- any TEAE,
- any post-treatment AE (displayed only for the Extension follow-up period),
- Severe TEAE,
- any TEAE assessed by the Investigator as related to linzagolix ((definite, probable, or possible relationship),
- any TEAE assessed by the Investigator as related to add-back therapy ((definite, probable, or possible relationship),
- any TEAE leading to permanent discontinuation of IMP,
- any serious adverse event (SAE),
- any serious treatment emergent adverse event (Serious TEAE),
- any non-serious TEAE
- any serious treatment emergent adverse event (SAE) related to linzagolix,
- any serious treatment emergent adverse event (SAE) related to add-back therapy,
- any fatal TEAE (where outcome is "Fatal")

In these tabulations, each subject will contribute only once (i.e., via the most related occurrence or the most intense occurrence) to each of the incidence rates in the descriptive analysis, regardless of the number of episodes experienced.

Adverse events are summarized by subject incidence rates, therefore, in any tabulation, a subject contributes only once to the count for a given adverse event (SOC or preferred term).

For the Extension treatment period, Extension follow-up period and combined Extension treatment and follow-up period, the number and percentage of subjects with any treatment-emergent adverse event, with any treatment-emergent adverse events assessed by the Investigator as related to treatment (definite, probable, or possible relationship), and with any treatment-emergent serious adverse event and with any treatment-emergent non-serious adverse event will be summarized by treatment group and overall, by SOC and PT. Tabulation by severity will also be made. In these tabulations, each subject will contribute only once (i.e., the most related occurrence or the most intense occurrence) to each of the incidence rates in the descriptive analysis, regardless of the number of episodes.

CRS-BS-TP-000005 V 2.0

The number of events will be also displayed for summaries on TEAE and for analysis of TEAE and non-serious TEAE by SOC and PT.

The ongoing status of each Adverse Event will be derived based on Adverse Event Outcome as the following:

AE Outcome	AE Ongoing Status
Fatal	No
Not recovered/not resolved	Yes
Recovering/resolving	Yes
Recovered/resolved	No
Recovered/resolved with sequelae	No
Unknown	Unknown
Missing	Missing

The ongoing status collected in eCRF will be ignored.

No formal hypothesis-testing analysis of adverse events incidence rates will be performed.

All adverse events occurring on study will be listed in subject data listings.

By-subject listings also will be provided for the following: Treatment Emergent Adverse event, serious Treatment Emergent adverse events; Treatment Emergent adverse events leading to permanent discontinuation of IMP and leading to permanent discontinuation of IMP leading to death.

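### SAP 6.6.1 starts the TEAE window at the first extension dose, yet orders three TEAE tables that cover the main study, two of them with subjects who never entered the extension

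*SAP*

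**What the plan says.** SAP 6.6.1 has one TEAE definition with two limbs. The first covers "AEs with a start date on or after the first dose of extension study drug through 30 days after discontinuation of study drug", with the Month 12 visit date as an alternative limit. The second covers "any event that was present at Month 6 but worsened in intensity or was subsequently considered" related to study drug, up to the end of the extension study. Its scope is general: "All analysis described below will be based on the Treatment Emergent Adverse Events (TEAEs), unless otherwise specified".

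The section then lists six TEAE tables by period and population. Three include main-study time:

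- for extension entrants only, "Combined Main treatment period and Extension treatment period on Extension Safety Analysis Set";
- for entrants and non-entrants together, "Combined Main treatment period and Extension treatment period on Safety Analysis Set";
- for the longest window, Day 1 of the main study to the end of extension follow-up, or "end of Main follow-up period for subjects not entering extension, on Safety Analysis Set".

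For the Safety Analysis Set tables, 6.6.1 notes that exposure differs: "up to 6 months for subjects not in extension, up to 12 months for subjects entering extension". It gives them five columns: the two linzagolix/linzagolix groups, the two Placebo/linzagolix groups, and Placebo.

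The overall summary is ordered for every period: "For all study periods, an overall summary table will be prepared presenting, by treatment group, the number and percentage of subjects with" a list of 13 AE categories.

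**The concern.** The tables and the definition do not match. A table headed main plus extension, or Day 1 to end of follow-up, should show what emerged on treatment over that whole time. Under the only definition supplied, main-study events enter these tables only if they were still present at Month 6 and then worsened or were reclassified as drug-related. Subjects who stopped at or before Month 6 have no extension dose, so the first limb cannot apply to them, but they are in the denominators of two tables.

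At stake is the cumulative treatment-emergent safety picture. The TEAE rows would understate incidence over up to 12 months. The understatement would differ by column, because non-entrants sit in some columns and not in others.

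**Working it through.** **Step 1. Can other text supply the missing rule?**

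- SAP 6.6.1 refers to section 5.2 for the periods. Section 5.2.1 defines only the extension treatment and extension follow-up periods. It defines the end-of-extension-study date only for subjects who entered, so the Month 6 limb has no end date for a non-entrant.
- SAP 4.1 defines seven analysis sets. Safety Analysis Set is not one of them. It may come from the main-study SAP, which is not among the documents. Section 6.6.1 does not cite that SAP, although 6.3.4, 6.3.6 and 6.4.2.1 do so where they rely on it.
- SAP 6.2.6.2, on missing dates, treats a non-entrant's completely undated AE as treatment-emergent from the first main-study dose, unless it ended before that dose. It does the same for an entrant's undated AE that ended before the first extension dose. A fully dated Month 2 event in either subject, resolved before Month 6, is not a TEAE under 6.6.1. The two sections therefore conflict.

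**Step 2. How many rows depend on the flag?** The 13 categories include 10 that need it: any TEAE; severe; related to linzagolix; related to add-back; leading to discontinuation; serious; non-serious; serious related to linzagolix; serious related to add-back; fatal. Three do not: any AE, any post-treatment AE, any SAE. In the two main-plus-extension treatment tables the post-treatment row is not displayed, which leaves 10 of 12.

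**Step 3. Planned numbers.** The inputs are in SAP 2.2: 450 randomized, 80% completing, up to 80% of completers entering.

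- Completers: 450 × 0.80 = 360. Entrants: 360 × 0.80 = 288. Both match the plan's figures.
- Non-entrants: 450 − 288 = 162, and 162/450 = 36%, taking all 450 as dosed. They are 450 − 360 = 90 non-completers and 360 − 288 = 72 completers who do not enter.
- If the Month 6 limb is read to reach those 72 completers, 90/450 = 20% still cannot qualify.

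**Step 4. Effect by column**, assuming equal entry across arms (150 per arm, 1:1 split of former placebo subjects) and linzagolix non-entrants placed in the linzagolix/linzagolix columns, since no other column is listed for them:

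| Column | Subjects | Entrants | TEAE rate p among entrants shown as |
|---|---|---|---|
| Each linzagolix/linzagolix | 150 | 150 × 0.64 = 96 | 96/150 × p = 0.64p |
| Each Placebo/linzagolix | 96/2 = 48 | 48 | p |
| Placebo | 150 − 96 = 54 | 0 | about 0 |

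With p = 50% in all entrants (illustrative), the linzagolix/linzagolix columns show 0.64 × 50% = 32% and the Placebo/linzagolix columns 50%.

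**Step 5. Range.** Both rates are planning assumptions, and 288 is an upper estimate at 80% completion. The other scenarios below are assumed:

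| Completion | Entry among completers | Entrants | Non-entrants | Factor |
|---|---|---|---|---|
| 80% | 60% | 216 | 234 (52%) | 0.48 |
| 80% | 70% | 252 | 198 (44%) | 0.56 |
| 80% | 80% | 288 | 162 (36%) | 0.64 |
| 90% | 80% | 324 | 126 (28%) | 0.72 |

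These factors cover non-entrants only. The further loss of entrants' own Month 1 to 6 events affects all three tables and cannot be sized from the documents. As an indication only, protocol 5.5.3 reports that in the Phase 2b study 616 of 846 TEAEs (72.8%) arose in the first 24 weeks.

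**The case against.** The strongest reply is that this is a drafting omission with a visible intent. SAP 6.2.6.2 imputes AE onset dates only to identify treatment-emergent events, and it sends some partial dates, as well as completely missing ones, to the first main-study dose. That would have little purpose if only the extension flag existed. Safety Analysis Set also looks like a main-study term, and a programmer may carry the main-study TEAE flag forward. The dilution and the near-zero Placebo column would then never appear. This stands as evidence of intent, and the stated effects do follow from a literal reading. But it does not supply a rule: the imputation section fixes dates and defines no TEAE window. A safety flag should not rest on an undocumented choice.

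Second, the columns are unlike by construction. The Placebo/linzagolix columns hold only subjects who completed six months and entered, while the linzagolix/linzagolix columns mix entrants with non-entrants. Correcting the flag would not make them comparable, and no AE comparison is tested. That is right, but the definition adds an avoidable artefact to a difference the SAP already acknowledges.

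Third, the damage is contained. The any-AE and any-SAE rows, the Day 1 all-AE table, the AE listing and the extension-only TEAE tables are all intact. That also stands, and it limits the severity.

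**Conclusion.** The concern holds. As written, 6.6.1 applies an extension-anchored TEAE definition to three of its six TEAE tables where it does not fit. In all three, Month 1 to 6 events that resolved or did not change are dropped. In the two Safety Analysis Set tables, non-entrants also dilute the linzagolix/linzagolix percentages, by a factor of 0.64 at the planned size, and the Placebo column is emptied. Those sizes rest on the planning rates, all 450 subjects being dosed, equal entry across arms and the natural reading of the Month 6 limb. A wider reading lowers the share that cannot qualify from 36% to 20% and is itself an ambiguity. With equal entry, the ratio between the two linzagolix/linzagolix columns is preserved. The size in the actual trial is not known from the documents.

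The body of 6.6.1 orders tables by system organ class and preferred term for the extension periods only, so on that text the defect lies in the overall summary rows. If such tables are also produced for all periods, as the V3.0 entry in SAP section 7 describes, it reaches them too. This should be fixed, but it does not touch the efficacy results or the extension-only safety tables.

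**What to change.** Use a period-specific TEAE flag.

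- Keep the present definition for the extension-only tables.
- For the three tables that include the main study, count onset on or after the first main-study dose through 30 days after the subject's last dose. For entrants that is the last extension dose, with the Month 12 visit limit kept; for non-entrants it is the last main-study dose. Also count events present at main-study baseline that worsened or were later judged drug-related. If the main-study SAP already has a TEAE definition, cite it and confirm that it serves these tables.
- State how events in a gap between main and extension dosing are flagged. SAP 4.2 foresees gaps of 28 days or more.
- Footnote that events during placebo treatment count in the Placebo/linzagolix columns.
- Make 6.2.6.2 refer to the same flag.
- Define Safety Analysis Set and the main treatment period in this SAP, or cite where they are defined.
- State in 6.6.1 which periods get tables by system organ class and preferred term, so that the right flag is used wherever they are produced.

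The cost is SAP wording and one additional derived flag. No new data are needed, and the extension-only tables do not change.
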